9.2. Efficacy

9.2.1. Evaluations

9.2.1.1. Hospital Recovery Scale Assessment

The hospital recovery scale assesses a subject's clinical status and will be assessed as the subject's condition on Day 6 as the primary endpoint. The hospital recovery scale will be assessed on Days 2 to 14 (excluding the primary time point) as secondary endpoints.

The hospital recovery scale provides 6 mutually exclusive conditions ordered from best to worst, and the score reflects the subject's worst situation on the day of assessment:

1. Not Hospitalized
2. Non-ICU Hospitalization, Not Requiring Supplemental Oxygen
3. Non-ICU Hospitalization, Requiring Supplemental Oxygen
4. Admitted to the ICU, Not Requiring Invasive Mechanical Ventilation
5. Requiring Invasive Mechanical Ventilation
6. Death

The hospital recovery scale categories are defined below. For ease of categorization, the categories are defined from worst to best.

Hospital Recovery Scale: Definitions^a

6. Death
 - Subject died at any time on the day of assessment or earlier (all-cause mortality).
5. Requiring invasive mechanical ventilation
 - Any oxygen support requiring intubation or extracorporeal oxygenation
 - Invasive mechanical ventilation is used at any time on the day of assessment.
4. Admitted to the ICU, not requiring invasive mechanical ventilation
 - Subject met either of the 2 following criteria:
 - In the ICU (and ICU level of care is required during the day of assessment)
 - On the hospital ward, with or without supplemental oxygen, but deemed to require ICU level of care at any time during the day of assessment (eg, not transferred to ICU due to bed availability)
 - Requiring ICU level of care is defined by:
 - Some specific conditions:
 - Treatment of acute unstable arrhythmias
 - Treatment of complicated acid-base or electrolyte imbalances
 - Large volume resuscitation
 - Utilization of intravenous vasoactive medications

^a If a subject was discharged from the hospital “Against Medical Advice” on the day prior to the day of assessment, the subject will be categorized per the definitions above in the category the subject was in at the moment of discharge “Against Medical Advice”. The hospital recovery scale category will be considered missing on subsequent days.

If a subject declines medically-indicated mechanical ventilation or care that requires an ICU level of intervention, the subject will be categorized according to the care they would otherwise have received on that day.

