- Non-ICU hospitalized on the day of assessment (including readmittance), not ready for discharge during the whole day of assessment, as judged by the investigator and supplemental oxygen is required by the subject
- In the ICU but there is no medical reason to be in the ICU during the day of assessment, and supplemental oxygen is required by the subject

Requiring supplemental oxygen is defined by:

- Receiving supplemental oxygen through a face mask or nasal cannula and not being able to sustain a blood oxygen saturation of $\geq 94\%$ when breathing room air for 15 minutes at any time on the day of assessment.
- If supplemental oxygen was provided chronically pre-influenza infection (based on medical history), that amount of supplemental oxygen is exceeded to prevent hypoxia, tachypnea or dyspnea at some point on the day of assessment.
- Not receiving supplemental oxygen and either:
 - Having a blood oxygen saturation of $< 94\%$ when breathing room air for 15 minutes at any measurement on the day of assessment, or
 - In case of known pre-influenza $SpO_2 < 94\%$ (e.g., due to COPD), the current blood oxygen saturation on room air is lower than pre-influenza infection levels by at least 3%.

2. Non-ICU hospitalization, not requiring supplemental oxygen

Subject met either of the 2 following criteria:

- Non-ICU hospitalized on the day of assessment (including readmittance) and not ready for discharge during the whole day of assessment, as judged by the investigator
- In the ICU but there is no medical reason to be in the ICU during the day of assessment

1. Not hospitalized

Any of the following:

- Discharged from the hospital before the day of assessment
- Hospitalized at the day of assessment but ready for discharge on both the day of assessment and the day prior, as judged by the investigator (e.g., in case of lack of bed availability in a skilled nursing facility, lack of social support at home).

Notes: If a subject was discharged from the hospital “Against Medical Advice” on the day prior to the day of assessment, the subject will be considered as hospitalized (evaluating the other aspects of the HRS to define the correct category based on available data, e.g.: requiring supplemental oxygen, on the day of assessment). The hospital recovery scale category will be considered missing on subsequent days.

The HRS will be missing after a subject withdrew (except for withdrawal due to death) from the study.

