5. Requiring invasive mechanical ventilation;

When CMSTDTC<=(date of assessment) <=CMENDTC where CMADMTP="INVASIVE MECHANICAL VENTILATION"

And CMADMDS in ('Through Endotracheal tube' 'Through Tracheostomy tube' or 'Through ECMO')

4. Admitted to the ICU;

From the HO data set:

hostdy <=(day of assessment)<=hoendy
hoterm = 'ICU'

From the SS data set:

SSTESTCD= 'REQICU' and SSSTRESC='Y'
Or SSTESTCD= 'REASICU' and SSSTRESC='Y'
Or both REQICU and REASICU is missing and NOT (RDISHOSP = 'Y' on the day of assessment and RDISHOSP = 'Y' on the day (baseline visit) before)

OR

From the HO data set:

hostdy <=(day of assessment)<=hoendy
hoterm = 'WARD'

From the SS data set:

SSTESTCD='REASICU' and SSSTRESC='Y'
OR
SSTESTCD='REQICU' and SSSTRESC='Y'

3. Non-ICU hospitalization, requiring supplemental oxygen

Non-ICU hospitalization:

hostdy <=(day of assessment)<=hoendy
hoterm = 'Hospital inpatient Department (WARD)'
NOT (RDISHOSP='Y' on the day of assessment and RDISHOSP='Y' on day(baseline visit) before)

OR

hostdy <=(day of assessment)<=hoendy
hoterm = 'ICU'
NOT (RDISHOSP='Y' on the day of assessment and RDISHOSP='Y' on day(baseline visit) before)

OR

(day of assessment)=hoendy+1
RDISHOSP='N' on day(baseline visit) before

OR

In case re-hospitalization occurred (there is a day between the HOENDY of the previous record and HOSTDY of the next record)
(day of assessment) =HOSTDY (of the re-hospitalization)
NOT (RDISHOSP='Y' on the day of assessment and RDISHOSP='Y' on day(baseline visit) before)

AND

Requiring supplemental oxygen:

'Receiving supplemental oxygen through a face mask or nasal cannula and not being able to sustain a blood oxygen saturation of $\geq 94\%$ when breathing room air for 15 minutes at any time on the day of assessment.'

FAOBJ=CHRONIC OXYGEN USE and FAORRES='N'

CMADMTP in ("Non-Invasive Mechanical Ventilation", "Nasal Cannula", "Venturi Mask", "Simple Face Mask", "Nonrebreathing Face Mask with Reservoir and One-Way Valve".)

CMTRT=SUPPLEMENTAL OXYGEN and CMSTDTC <= date of assessment <= CMENDTC

VSOXYSAT in ('N' 'NA') at any time during the day of assessment (OR is missing)

OR

'If supplemental oxygen was provided chronically pre-influenza infection (based on medical history), that amount of supplemental oxygen is exceeded to prevent hypoxia, tachypnea or dyspnea at some point on the day of assessment.'

FAOBJ=CHRONIC OXYGEN USE and FAORRES='Y'

CMARTN = 'N'

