CMADMTP in ("Non-Invasive Mechanical Ventilation", "Nasal Cannula", "Venturi Mask", "Simple Face Mask", "Nonrebreathing Face Mask with Reservoir and One-Way Valve".) and CMTRT=SUPPLEMENTAL OXYGEN and CMSTDTC <= date of assessment <= CMENDTC

OR

'Not receiving supplemental oxygen and Having a blood oxygen saturation of <94% when breathing room air for 15 minutes at any measurement on the day of assessment'

No record in cm with oxygen supplementation

VSOXYSAT='N' at any time on the day of assessment OR [VSTESTCD='OXYSAT' and VSORRES<94% and VSOXSMRA='Y']

OR

'Not receiving supplemental oxygen and in case of known pre-influenza SpO2 <94% (eg, due to COPD), the current blood oxygen saturation on room air is lower than pre-influenza infection levels by at least 3%.'

No record in cm with oxygen supplementation

VSEVINTX= PRE-INFLUENZA INFECTION and VSTESTCD='OXYSAT' and 'VSORRES<94% and VSRMAIR='Y'

VSORRES and VSTESTCD=OXYSAT (of day of assessment) < [VSORRES and VSEVINTX= PRE-INFLUENZA INFECTION and VSTESTCD='OXYSAT' and VSRMAIR='Y' - 3]

2. Non-ICU hospitalization, not requiring supplemental oxygen

hostdy <=(day of assessment)<=hoendy

hoterm = 'Hospital inpatient Department (WARD)'

NOT (RDISHOSP='Y' on the day of assessment and RDISHOSP='Y' on day(baseline visit) before)

hostdy <=(day of assessment)<=hoendy

hoterm = 'ICU'

NOT (RDISHOSP='Y' on the day of assessment and RDISHOSP='Y' on day(baseline visit) before)

OR

(day of assessment)=hoendy+1

RDISHOSP='N' on day(baseline visit) before

OR

In case re-hospitalization occurred (there is a day between the HOENDY of the previous record and HOSTDY of the next record)

(day of assessment) =HOSTDY (of the re-hospitalization)

NOT (RDISHOSP='Y' on the day of assessment and RDISHOSP='Y' on day(baseline visit) before)

1. Not hospitalized

Some examples

Discharge against medical advice

If a subject is discharged 'against medical advice' on the day prior to the day of assessment, the subject will be considered as hospitalized (evaluating the others aspects of the HRS to define the correct category, e.g.: requiring supplemental oxygen, on the day of assessment)

We have a discharged against medical advice if on the day the subject is discharged (according to the HO dataset) the investigator indicated he is not ready and his SS status is discharged,

	Day 3	Day 4	Day 5	Day 6	Day 7	Day 8
Status (HO)	Hospitalized	Hospitalized	Hospitalized	Discharged	Home	Home
Case 1						

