ready (SS)	Not ready	Not ready	Not ready	Not ready	--	--
Status(SS)	hospitalized	hospitalized	hospitalized	Hospitalized	discharged	--
Against medical advice?					NO	
HRS	>1	>1	>1	>1	>1	HOME
Case 2						
ready (SS)	Not ready	Not ready	Not ready	Not ready	Ready	--
Status(SS)	hospitalized	hospitalized	hospitalized	Hospitalized	discharged	--
Against medical advice?					NO	
HRS	>1	>1	>1	>1	>1	HOME
Case 3						
ready (SS)	Not ready	Not ready	Not ready	Not ready	Not ready	--
Status(SS)	hospitalized	hospitalized	hospitalized	Hospitalized	discharged	--
Against medical advice?					NO	
HRS	>1	>1	>1	>1	>1	HOME
Case 4						
ready (SS)	Not ready	Not ready	Not ready	Not ready		--
Status(SS)	hospitalized	hospitalized	hospitalized	Discharged		

Against medical advice?				YES		
HRS	>1	>1	>1	>1	>1	Missing
Case 5						
ready (SS)	Not ready	Not ready	Not ready	Ready	--	--
Status(SS)	hospitalized	hospitalized	hospitalized	discharged		
Against medical advice?				NO		
HRS	>1	>1	>1	>1	HOME	HOME
Case 6						
ready (SS)	Not ready	Not ready	Not ready	Ready	--	--
Status(SS)	hospitalized	hospitalized	hospitalized	hospitalized	discharged	
Against medical advice?				NO		
HRS	>1	>1	>1	>1	HOME	HOME
Case 7						
ready (SS)	Not ready	Not ready	Ready	Ready	--	--
Status(SS)	hospitalized	hospitalized	hospitalized	hospitalized	discharged	
Against medical advice?				NO		
HRS	>1	>1	>1	HOME	HOME	HOME
Case 8						
ready (SS)	Not ready	Not ready	Not ready	--	--	--
Status(SS)	hospitalized	hospitalized	discharged	--	--	
Against medical advice?			NO			
HRS	>1	>1	>1	>1	HOME	HOME

Only in case 4 above we have a discharge against medical advice which would lead to missing values from day 8 onwards. The HRS on day 7 is defined by the other aspects of the HRS (requiring oxygen, ICU,..) on day 7 and not copied from day 6.

Requiring supplemental oxygen

	Case 1	Case 2	Case 3	Case 4	Case 5	Case 6
supplemental oxygen (CM)	YES	YES	NO	NO	NO	NO
Chronic oxygen use	No	yes	Not used	Not used	Not used	Not used
returned to prior level?	Not used	N	Not used	Not used	Not used	Not used
pre influenza infection levels	Not used	Not used	Not used	Not used	Not used	93
Oxysat record < pre-influenza level at any moment during the day	Not used	Not used	Not used	Not used	Not used	yes
sustain >94% Oxy sat (VSOXYSAT)	N' missing or 'NA'	N' missing or 'NA'	N' at any time during the day	Missing or NA	YES	Not used
Oxysat record <94% at any moment during the day	Not used	Not used	no	yes	yes	Not used

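### The day after discharge against medical advice, the SAP re-derives the recovery-scale score that the protocol carries over, so an ICU leaver cannot keep category 4 and an oxygen leaver may score 2

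*SAP*

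**What the plan says.** **Protocol 9.2.1.1, footnote to the scale definitions.** For AMA discharge on the day before assessment, "the subject will be categorized per the definitions above in the category the subject was in at the moment of discharge". Later days are missing.

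**SAP 5.2.1, notes under the definition.** For the same subject, hospitalization is assumed and the category comes from "evaluating the other aspects of the HRS to define the correct category based on available data", applied to the day of assessment. Later days are missing here too.

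**SAP Attachment 6, discharge examples.** For the one AMA example (Case 4, leaving on Day 6), the Day 7 score is "defined by the other aspects of the HRS (requiring oxygen, ICU,..) on day 7 and not copied from day 6".

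**SAP 5.2.2.** The estimand text says the scale reflects where a subject ought to be rather than where the subject physically is.

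**The concern.** The two documents give different primary-endpoint values for the same subject. The protocol leaves statistical detail to the SAP (section 11), and the SAP says it is to be read together with the protocol (section 1). Neither statement covers reversing an endpoint rule, and the SAP amendment history gives no reason for doing so.

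The SAP rule also sits badly with its own estimand. A person who left against advice should still be in hospital at the level of care they left. The protocol applies the same idea to subjects who decline ICU care or ventilation, scoring them by the care they would otherwise have had. SAP 5.2.1 does not repeat that rule.

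Under the SAP rule, a lack of next-day data is recorded as not needing oxygen. The result counts as an observed score, so the missing-data analyses do not test it.

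**Working it through.** **Which subjects matter for Day 6.** AMA discharge before Day 5 makes Day 6 missing in both documents; SAP 5.2.3 lists it as a reason for missingness. AMA discharge on Day 6 or later leaves the Day 6 score unaffected by the rule. That leaves AMA discharge on Day 5.

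**Attachment 6 on the day after discharge (`hoendy`+1), subject alive.**
- Category 5 needs an invasive-ventilation record spanning the day.
- Category 4 needs "hostdy <=(day of assessment)<=hoendy" in both its ICU and its ward branch. On `hoendy`+1 this is false, so category 4 cannot be assigned, although the Case 4 comment names ICU among the aspects evaluated.
- The branch for the next day, "day of assessment)=hoendy+1" with the subject not ready for discharge the day before, exists only under categories 3 and 2.
- Category 3 also needs evidence of oxygen need. One route is an oxygen record spanning the day ("CMTRT=SUPPLEMENTAL OXYGEN and CMSTDTC <= date of assessment <= CMENDTC"). The other is no oxygen record with a low room-air saturation that day: below 94%, or more than 3 points below a known low pre-influenza level.
- Category 2 takes the rest.

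**Data available on the next day.** The post-discharge schedule (Time and Events Schedule 2) has pulse oximetry at the Day 6 and Day 28 visits only. The Day 6 visit may be held on Day 7.

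**Scores on the day after AMA discharge, from coding these rules (no chronic oxygen use):**

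| Next-day data | SAP score | Protocol: left on ward oxygen | Protocol: left ICU needing ICU care |
|---|---|---|---|
| None; oxygen record closed | 2 | 3 | 4 |
| Room-air saturation 95%; oxygen record closed | 2 | 3 | 4 |
| Room-air saturation 91%; oxygen record closed | 3 | 3 | 4 |
| Oxygen record still open; no saturation | 3 | 3 | 4 |

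Two rows depend on how Attachment 6 is read. In the third, the condition that there is no oxygen record is taken to apply to that day; if it meant no record at any time, the score would be 2. The fourth follows the written rule and Case 1 of the oxygen examples; Case 7, as printed, answers no for a similar pattern.

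**Planned sample size, reproduced first.** Inputs from SAP 1.4 and 5.1.1: placebo Day 6 distribution 30/30/25/5/5/5%, a 38% reduction (odds ratio 0.62), two-sided 5%, 90% power, 1:1. The proportional-odds formula is N = 12(z₀.₉₇₅ + z₀.₉₀)² / [(ln OR)²(1 − Σp̄ᵢ³)], where p̄ᵢ is the mean of the two arms. An odds ratio of 0.62 gives a pimodivir distribution of 40.9/29.9/19.4/3.4/3.3/3.2%, and Σp̄ᵢ³ = 0.0825. Then N = 12 × 10.507 / (0.2285 × 0.9175) = 601.4 against the stated 600, and power at 600 is 89.9%. The conflict does not touch this calculation.

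**Size of the effect.** The AMA rates here are assumptions. Suppose a fraction of an arm leaves AMA on Day 5 and is scored 2 instead of 3. Refitting a treatment-only proportional odds model to the expected counts gives these common odds ratios (0.620 with no shift):

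| Fraction of arm shifted | Both arms | Pimodivir only | Placebo only |
|---|---|---|---|
| 0.5% | 0.619 | 0.614 | 0.625 |
| 1% | 0.618 | 0.608 | 0.630 |
| 2% | 0.617 | 0.597 | 0.640 |

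With 300 per arm, 2% is 6 subjects per arm.

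**The case against.** The strongest reply is that the SAP does not score these subjects blind. Someone who leaves on Day 5 has a clinic or home visit with pulse oximetry due on Day 6. Attachment 6 provides for records on or after the end of the hospital stay. A low saturation, or an oxygen record still open, keeps the subject in category 3. A normal room-air saturation on Day 6 is real information. The rule also keeps AMA leavers out of category 1. All of this stands.

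It defeats some stronger readings that a reader might infer:
- *Every such subject falls to category 2 for want of data.* The drop is conditional, as two of the four scenarios show for oxygen leavers.
- *Each affected subject moves one to three categories.* A subject who left in category 2, or on oxygen with a low next-day saturation, does not move. A three-category move would need someone on invasive ventilation to leave.
- *The same subject is misscored throughout Days 2 to 14.* The rule applies to one day per AMA discharge; later days are missing in both documents.

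The reply does not remove the conflict. It does not help the ICU leaver, who cannot score 4 whatever is recorded. It also does not help when the visit is missed or held on Day 7. For most other days in the Day 2 to 14 analyses no next-day oximetry is scheduled, although those analyses are outside the confirmatory hierarchy.

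**Conclusion.** The concern holds in this form: for the day after AMA discharge, SAP 5.2.1 and Attachment 6 contradict protocol 9.2.1.1 on the primary endpoint. A subject leaving the ICU while needing ICU care goes from 4 to 3 or 2. A subject leaving on oxygen stays at 3 or goes to 2, depending on what is recorded the next day, and 2 is the default when nothing is.

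The expected effect is small. It rests on an assumed AMA rate, on 3-to-2 shifts only, and on a model without the baseline score and strata that the SAP will include. At 2% the odds ratio hardly moves if the arms are alike (0.620 to 0.617), and moves to 0.597 or 0.640 if only one arm is affected. The documents give no reason to expect such an imbalance. The case for change is that a primary endpoint should have one definition, and that Attachment 6 cannot assign the ICU category its own comment refers to.

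**What to change.** Amend SAP 5.2.1 and Attachment 6, including the Case 4 comment, to the protocol rule. On the day after AMA discharge, assign the category held at the moment of discharge. Keep the existing rule that later days are missing.

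Copying the previous day's score would not do this. The daily score is the worst state of that day, and a subject moved from ICU to ward before leaving would be carried forward as 4. The derivation should use the location, ICU need, oxygen record and latest saturation that applied at departure, and state what happens when a time is missing.

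The imputation analyses should not be cited as cover for the later missing days. SAP 5.2.3 runs them only if more than 10% of Day 6 values are missing, and SAP 5.3.2.1 excludes them for the other days.

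The cost is a short SAP amendment and a modest change to derivation code, before unblinding, with no new data collection planned. A count by arm of subjects scored under this rule on Day 6 would let readers judge its effect.

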5.2.2. Estimand

The population of interest is hospitalized subjects between 13 to 85 years old with a confirmed influenza A infection.

The primary variable is the hospital recovery scale as assessed on Day 6 and will be compared between pimodivir and placebo on top of SOC. The hospital recovery scale is an ordinal mutually exclusive scale of six categories (death, requiring mechanical ventilation, requiring ICU, non-ICU hospitalized requiring supplemental oxygen, non-ICU hospitalized not requiring supplemental oxygen and non-hospitalized).

The intercurrent event of the use of influenza antivirals as part of SOC is handled in a treatment policy strategy as the primary endpoint is derived in the same way irrespective of the components of SOC. Treatment discontinuation is an intercurrent event that is also handled in a treatment policy strategy. Death as intercurrent event is handled in a composite strategy as it is one of the categories of the HRS. Other factors as for example bed availability that can influence the status of the subject are intercurrent events that are also handled with the composite strategy as the HRS accounts for the status of where the subject ‘should be’ instead of where the subject physically is.

The common odds ratio estimated by a proportional odds model is used as the population-level summary. If the assumption (by testing the parallel slopes for the treatment effect only) of the proportional odds would not hold for the treatment effect, the Van Elteren test will be used in a sensitivity analysis and the resulting p-value would be used in the formal testing. A second sensitivity analysis is conducted to handle missing data by an MAR/MNAR multiple imputations method. This is done for all missing HRS values on day 6 and separately for HRS values on day 6 that are missing due to COVID-19 and for HRS values that are missing not due to COVID-19.

5.2.3. Analysis Methods

A proportional odds model will be used as primary model to analyze the hospital recovery scale on Day 6, modeling the common odds ratio of improvement on the ordinal scale of active treatment versus placebo. The model will include treatment, hospital recovery scale category at baseline and the stratification factors (NEWS2 category at screening, type of baseline SOC, and time since onset of influenza symptoms). In a first step equal slopes (i.e. proportional odds) for the treatment effect only and unequal slopes for the other covariates, will be modeled. If this model does not fit a full

proportional odds model will be applied, i.e. implying proportional odds for all covariates in the model. The common odds ratio from the final model will be considered as the estimate of the treatment effect. The actual values of the stratification factors will be used for all models, not as randomized. The proportional odds model will be defined in such a way that a common odds ratio smaller than 1 indicates larger improvement in the pimodivir treatment group.

Graphical displays and tabulations will be provided showing the proportion of subjects per hospital recovery scale category and day. Also, shift tabulations will be provided of the baseline hospital recovery scale category versus the post-baseline hospital recovery scale category, per day.

The proportional odds assumption will be assessed by testing for parallel slopes for the treatment effect only.

In addition, each of 5 dichotomizations of the hospital recovery scale, ie,

- Not hospitalized, vs worse (ie, hospitalized)
- Non-ICU hospitalized without supplemental oxygen (or better), vs worse
- Non-ICU hospitalized with supplemental oxygen (or better), vs worse
- In the ICU without invasive mechanical ventilation (or better), vs worse
- Invasive mechanical ventilation (or better), vs worse (ie, died)

will be analyzed using a logistic regression model, including treatment, hospital recovery scale category at baseline and stratification factors.

The hospital recovery scale will also be analyzed using the Van Elteren test with strata defined by the stratification factors^[3, 6].

A table will be created showing the number (%) missing HRS values at day 6 overall and by reason: study discontinuation: due to COVID-19 and not due to COVID-19, discharged against medical advice prior to day 5 and subjects that have no confirmed influenza A.

In case of more than 10% missing data on Day 6: multiple imputation will be employed as sensitivity analyses for the proportional odds model of the HRS (excluding the subgroup analyses), under the missing-at-random (MAR) assumption and missing-not-at-random (NMAR) assumption.

- If more than 5% of the patients have a missing HRS value due to COVID-19 (i.e.: discontinued due to COVID-19), the multiple imputation method will also be done separately on these subjects.
- If more than 5% of the patients have a missing HRS values unrelated to COVID-19, then also multiple imputation will be done separately in this group.

The Markov Chain Monte Carlo (MCMC) method will be used to create a number of multiple imputation datasets with monotone missingness in the clinical outcomes (baseline until Day 14). The number of imputation datasets will be the same as the percentage of missing data^[10]. For MAR assumptions, a monotone ordinal logistic regression imputation model will be used to complete the remaining missing clinical outcomes.

For the NMAR assumption, the imputed datasets obtained from the MAR assumption described above will be used, but with a structural shift in hospital recovery scale category on Day 6 of the imputed values, to introduce non-ignorable missing patterns:

- To reflect missingness patterns as a result of study discontinuation due to a dissatisfying treatment effect or safety issues in the placebo treatment group, the following shifts will be applied in the placebo treatment group only:
 - 1 category down, eg, from ‘1. Not hospitalized’ to ‘2. Non-ICU hospitalization, not requiring supplemental oxygen’
 - 2 categories down, eg, from ‘1. Not hospitalized’ to ‘3. Non-ICU hospitalization, requiring supplemental oxygen’
- To reflect missingness patterns as a result of study discontinuation due to a dissatisfying treatment effect or safety issues in the pimodivir treatment group, the following shifts will be applied in the pimodivir treatment group only:
 - 1 category down, eg, from ‘1. Not hospitalized’ to ‘2. Non-ICU hospitalization, not requiring supplemental oxygen’
 - 2 categories down, eg, from ‘1. Not hospitalized’ to ‘3. Non-ICU hospitalization, requiring supplemental oxygen’

In all cases, ‘6. Death’ will be the worst hospital recovery scale category after imputation and structural shift and ‘1 Not hospitalized’ will be the best hospital recovery category after imputation and structural shift.

The models fitted using the multiple imputation datasets will be the same as the final model on the actual data. The results from the models on the multiple imputation datasets will be combined taking into account the between and within variation of the results.

The analyses on the primary endpoint will be repeated by subgroups for efficacy as defined in Section 2.3. The final model above will be repeated adding these subgroups (defined in Section 2.3) as an additional covariate and interaction with treatment. Per subgroup the common odds ratio and the odds ratios calculated for the dichotomizations will be derived from these models. In addition, for each category in a subgroup, the Van Elteren test with strata defined by the stratification factors will be repeated.

